## Protocol Summary/Submission Application

excitatory pathways in the brainstem and spinal cord (10). PSH is characterized by a constellation of symptoms such as tachycardia, tachypnea, hypertension, hyperthermia, rigidity, tremors, sweating, and pupillary dilation as a result of sympathetic hyperactivity due to the brain injury (1,5,7,8). Research on PSH has been hampered by lack of a uniform definition and use of various terms such as neurostorming, dysautonomia. Consensus diagnostic criteria and a scoring algorithm (CFS) were developed in 2014 (1) (Table 1a,1b). PSH increases the risk for secondary brain injury and is associated with worse functional outcomes, longer hospitalization and higher healthcare costs (2,3,7,11). Appropriate treatment of PSH is important for patient comfort and to prevent secondary brain damage (12,13). Currently, PSH is treated using a combination of multiple neurotropic medications (narcotics, benzodiazepines, sympatholytics, gabapentin, muscle relaxants etc.) that can result in complications due to their side effects such as excessive sedation, respiratory depression, drug dependence, and constipation. Some of these medications necessitate longer ICU stays due to their CNS depressant effects thus potentially increasing healthcare costs (3). There has been very little research into novel ways of treating PSH other than the use of various neurotropic medications (14,15).

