### **E. Design and methods (including experimental design, technical details and laboratory methodology):**

#### **Design & Methods**

In this prospective unblinded pilot study we will enroll eligible patients until 20 parent/child dyads complete the study. It is expected many of the consented patients will not meet the eligibility criteria of CFS score > 6 (moderate severity of PSH). Those children will be considered Screen Failures and their parents/LAR told they are ineligible to continue in the study. Children admitted to the PICU at CW aged 2-17 years with ASBI and symptoms of PSH with a CFS score > 6 (moderate severity of PSH) will be eligible for inclusion. Exclusion criteria include age < 2 years (small ears thus less surface area to apply the leads), ear deformity or severe dermatitis of ear lobes, intractable seizures, heart block, patients with other implantable devices (cardiac pacemaker, vagal nerve stimulator, etc.) or known pregnancy.

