#### **Medication detail during study treatment:**

No additional maintenance medications (propranolol, bromocriptine, dantrolene, gabapentin, baclofen) will be allowed to be initiated for the first 12 hours after initiation of PENFS. Patients could continue to receive rescue medications (morphine, benzodiazepines such as lorazepam, midazolam, diazepam, clonidine) during this period for break through symptoms or remain on maintenance medications that were already in

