### **Aim 3a: Evaluate the change in autonomic balance with use of PENFS device**

**Methods:** We will use two separate validated modalities to evaluate the autonomic activity/balance in response to use of the device – HRV and Pupillometry. HRV denotes the beat-to-beat variability in the R-R interval on the EKG. Cardiac pacemaker automaticity is continuously altered and regulated by the autonomic nervous system (ANS). The parasympathetic system regulates HR on a beat-to-beat basis whereas the sympathetic system has slower onset but longer duration of action (16-18). Decreased HRV parameters has been shown to be associated with increased 30-day mortality in critically ill patients (19). Children with PSH were shown to have significant differences in HRV parameters compared to controls (20). We will calculate time-domain (mean heart rate, standard deviation of all average R-R intervals (SDNN), root mean square of the successive differences (RMSSD), physical stress index (PSI), approximate entropy (ApEn); successive R-R interval difference (SRD)) and frequency-domain indices (total power (TP), high frequency (HF), low frequency (LF), normalized HF, normalized LF, and LF/HF ratio) and compare the 12-hour period before and after placement of the PENFS device. Three separate 5-minute segments of continuous EKG tracings at rest (lying in bed) and body temperature 36-37.5C will be identified for both periods for comparison. Similarly, we will compare the pupillometry parameters along with direction of change before and after device placement.

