### **Aim 3b: Evaluate feasibility of measuring PENFS effectiveness in treating PSH by a decrease in medication use**

**Methods:** The maintenance medications and the number of doses and type of rescue medications administered will be collected for every 24 hours (0-24h, 25-48h, 49-72h, 73-96h, 97-120h, 121-144h, 145-168h, 169- 192h) for the enrolled patients. These will be compared to a historical cohort of PSH patients. The historical cohort will consist of PSH patients (2-17 years old) identified using the ICU Neurology administrative dataset from January 2018 – August 2021. This dataset will be used to identify ASBI patients who likely developed PSH. Eligible patients with PSH will be identified and relevant data collected by individual chart review. During this period all the PSH patients were followed by ICU Neurology thus ensuring a uniform approach to their treatment. We have also developed a practice guideline for treatment of PSH that will ensure uniform treatment of these patients during the study period. Similar to Aim 2a, we will examine the need for additional maintenance medications or change in frequency of rescue medications with discontinuation of the device. We hypothesize that, with discontinuation of the device, the patients may experience worse PSH symptoms as demonstrated by increasing CFS score and need for additional maintenance and/or rescue medications.

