## Protocol Summary/Submission Application

*Hypothesis 1:* The number approached and consented will be tracked. Reactions/ adverse events will be summarized and reasons for early termination, if any, evaluated.

*Hypothesis 2a, 2b:* The scoring tool will be adapted for the appropriate age range of the patient (Table 2). We aim for at least 80% scoring ( $\geq 8/10$  scheduled scoring per protocol while the device is worn). The association of the score and the number of doses of maintenance and rescue medications will be summarized with a spearman correlation and exact 95% Confidence intervals (CI).

*Hypothesis 3a:* HRV and Pupillometry measures will be tracked over time with any loss of data recorded with reasons. Wilcoxon Rank Sum test will be used to compare the mean  $\pm$ SD for the parameters for the 12-hour periods before and after device placement.

*Hypothesis 3b:* The number of doses of maintenance and rescue medications for control of PSH symptoms will be compared to historic data using a t-test or non-parametric Mann Whitney. Further a classification tree will be used to evaluate the effect of demographics, clinical history and use of PENFS.

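### Aim 3a gives no rule or masking for choosing the three 5-minute HRV segments and does not tie them to rescue doses, so either could create or hide the before/after change

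*Combined protocol and SAP*

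**What the plan says.** The Aim 3a methods list time-domain and frequency-domain HRV indices and say the team will "compare the 12-hour period before and after placement of the PENFS device". The data come from a small sample of the tracing: "Three separate 5-minute segments of continuous EKG tracings at rest (lying in bed) and body temperature 36-37.5C will be identified for both periods". Nothing further is said about who identifies the segments, how three are chosen when more qualify, or what happens when fewer than three do.

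Other parts of the plan bear on this:

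- **Blinding (Design & Methods).** "In this prospective unblinded pilot study we will enroll eligible patients until 20 parent/child dyads complete the study".
- **Table 3.** As the table reads after extraction, HRV is marked at -12 to 0 h, 0 h, 6 h and 12 h. The marks are not linked to the three segments.
- **Rescue drugs (Medication detail during study treatment).** For the first 12 hours after placement: "Patients could continue to receive rescue medications (morphine, benzodiazepines such as lorazepam, midazolam, diazepam, clonidine) during this period for break through symptoms".
- **Recording of drugs (Aim 3b).** "The maintenance medications and the number of doses and type of rescue medications administered will be collected for every 24 hours". Table 3 adds medication entries at -12 to 0 h and 12 h. No dose time is tied to an HRV segment.
- **Analysis (Hypothesis 3a).** "Wilcoxon Rank Sum test will be used to compare the mean" and SD of each parameter between the two periods. No covariate is named. Lost HRV data are to be recorded with reasons.
- **Missing data (Data analysis overview).** MAR is assumed in general, with imputation or mixed models and a sensitivity analysis.
- **Background.** The listed PSH symptoms are "tachycardia, tachypnea, hypertension, hyperthermia, rigidity, tremors, sweating, and pupillary dilation".

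**The concern.** Aim 3a supplies the mechanistic evidence. It hypothesises a directional result, a rise in parasympathetic tone, and the Innovation section presents HRV as an objective measure. That objectivity depends on how the tracing is sampled. A team following the text exactly may look at an unmasked tracing, know which period it comes from, and settle on three stretches that meet the rest and temperature conditions. Any lean in that choice, deliberate or not, passes straight into the period mean.

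Rescue drugs raise a second problem. The Background itself calls clonidine sympatholytic, so a segment recorded soon after a dose may show the very change that would be credited to the device. The bias can go either way. More recent doses in the after segments could mimic an effect; more in the before segments could hide one. The plan acknowledges confounding by maintenance drugs for the CFS trend (Aim 2b) but says nothing comparable about rescue drugs and HRV.

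**Working it through.** The plan states no HRV variance, effect size, alpha or power, so there is no figure to reproduce. The checks below are arithmetic on the plan's text, followed by illustrations on stated assumptions.

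**1. Fraction sampled.** 3 × 5 = 15 minutes out of 12 × 60 = 720, so 15/720 = 2.1%. Equivalently, 720/5 = 144 non-overlapping segments, of which 3 are used.

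**2. Does Table 3 supply the rule?** After placement it marks 0, 6 and 12 h, which could be read as three sampling times. Before placement it marks only the interval -12 to 0 h, with no clock times, and the 0 h mark could belong to either period. On that reading the after segments would have fixed times and the before segments would not. Table 3 therefore does not give one rule for both periods.

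**3. Temperature band.** On the CFS, temperature scores 0 below 37, 1 for 37–37.9, 2 for 38–38.9 and 3 from 39. Within 36–37.5 only 0 or 1 is possible, so all time at 38 or above is excluded, in both periods alike. A child can enrol without fever, because the other five items reach 5 × 3 = 15 and the threshold is a score above 6. The band thus removes fever from the comparison. It may also leave a child with sustained fever short of three segments.

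**4. Size of a selection effect (illustration).** Assume segments within a period are independent and normal with SD 1, and the three most favourable of m qualifying segments are taken. The expected shift is the mean of the top three expected order statistics:

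- m = 4: (1.029 + 0.297 − 0.297)/3 = 0.34 SD
- m = 5: (1.163 + 0.495 + 0)/3 = 0.55 SD
- m = 6: (1.267 + 0.642 + 0.202)/3 = 0.70 SD

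**5. What that does to a test (illustration).** Simulation with 20 children, no device effect, 3 random segments before, the most favourable 3 of m after, two-sided 0.05 and 2,000 runs. The between-patient SD was 0.5, 1 or 2.

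| After segments | Paired signed-rank, false positives | Planned rank-sum, between-patient SD 0.5 / 1 / 2 |
|---|---|---|
| 3 of 3 (no choice) | 4.6–5.0% | 1.2% / 0% / 0% |
| 3 of 4 | 45–46% | 22% / 3% / 0% |
| 3 of 5 | 84–86% | 66% / 21% / 0.5% |
| 3 of 6 | 97–98% | 89% / 48% / 1% |

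The rank-sum test ignores pairing, so between-patient spread masks the bias in the p-value. The estimated shift is biased by the same amount whichever test is used.

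**6. Rescue dose (illustration).** Suppose a dose moves HRV by d SD and affects a fraction f more of the after segments than of the before segments. The shift is d × f. With d = 0.5 and f = 0.33 it is about 0.16; with d = 1 and f = 0.67 it is 0.67. Across that range, with between-patient SD 1, simulated false-positive rates were 13–90% for the paired test and 0.4–36% for the rank-sum test.

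**The case against.** This is a convenience pilot of 20, described as not powered for efficacy. Aim 3a is one of several exploratory aims, and pupillometry is a second modality. The rest and temperature conditions are sensible controls, lost HRV data are recorded with reasons, and a missing-data sensitivity analysis is planned. All of that stands and limits the weight of the point. None of it supplies a selection rule, masking or a link to dose times.

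Some stronger readings are tempting, but the documents do not support them:

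- **That fever drives the before/after difference.** The same band applies to both periods, so it controls temperature.
- **That the sickest children drop out of a paired comparison.** The planned test is an unpaired rank-sum, and mixed models or imputation are allowed, so a child lacking segments in one period need not be lost. No frequency of such children is given, PSH is paroxysmal, and a high CFS score does not require fever.
- **That segments will be hand-picked for a favourable result.** The text says only that they will be identified. The defect is an unstated rule, and nothing suggests the selector will see computed HRV values.
- **That the SD shifts above are bounds or estimates.** The numbers of qualifying segments are assumed. More choice, or opposite leanings in the two periods, would give larger shifts; haphazard choice would give none.

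**Conclusion.** The point holds as a gap in the sampling and analysis rule. Three segments covering 2.1% of each period are chosen without a stated rule or masking in an unblinded study, without a link to Table 3 and without regard to rescue-dose timing. A before/after HRV difference, or its absence, could then reflect selection or dosing rather than the device. The size and direction of any bias cannot be determined from the documents. The 0.34 to 0.70 SD shifts assume independent segments and fully favourable choice in one period only.

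On temperature, the remaining concern is missingness. Children with sustained fever may have fewer than three qualifying segments, and that loss may depend on severity, which strains the MAR assumption. It should be corrected because it is cheap and because a reproducible extraction rule is itself a useful product of a feasibility study. It does not threaten the trial's main feasibility aims.

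**What to change.** 1. **Selection rule (Aim 3a methods).** Replace the wording that segments will be identified with one rule for both periods. Divide each 12-hour period into three 4-hour blocks and take one qualifying segment per block by seeded random draw, before any HRV index is computed. Mask the person who confirms rest and signal quality to period. Reconcile Table 3 with this, stating whether its 0, 6 and 12 h marks are sampling times and to which period 0 h belongs.
2. **Fewer than three segments.** Use those available and report, by period, how many children are affected.
3. **Rescue doses.** Take the time of the last rescue dose before each segment from the medication record. Add a sensitivity analysis with time since dose as a covariate in the mixed model the plan already foresees, fixing in advance how segments with no preceding dose are coded. Keep it as a sensitivity analysis, since rescue use after placement may itself respond to the device.
4. **Temperature.** Keep the band for the main analysis and add a secondary analysis without it.

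The cost is abstracting dose times for the two 12-hour periods, arranging the masked check, and accepting that some blocks will have no qualifying segment. The EKG is already recorded, and no patient procedure or treatment rule changes.

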### **Aim 3b: Evaluate feasibility of measuring PENFS effectiveness in treating PSH by a decrease in medication use**

**Methods:** The maintenance medications and the number of doses and type of rescue medications administered will be collected for every 24 hours (0-24h, 25-48h, 49-72h, 73-96h, 97-120h, 121-144h, 145-168h, 169- 192h) for the enrolled patients. These will be compared to a historical cohort of PSH patients. The historical cohort will consist of PSH patients (2-17 years old) identified using the ICU Neurology administrative dataset from January 2018 – August 2021. This dataset will be used to identify ASBI patients who likely developed PSH. Eligible patients with PSH will be identified and relevant data collected by individual chart review. During this period all the PSH patients were followed by ICU Neurology thus ensuring a uniform approach to their treatment. We have also developed a practice guideline for treatment of PSH that will ensure uniform treatment of these patients during the study period. Similar to Aim 2a, we will examine the need for additional maintenance medications or change in frequency of rescue medications with discontinuation of the device. We hypothesize that, with discontinuation of the device, the patients may experience worse PSH symptoms as demonstrated by increasing CFS score and need for additional maintenance and/or rescue medications.

### **Data collection & Management**

#### Screening & Consent:

We will screen all ASBI patients who appear to have symptoms of PSH during their PICU stay. If they meet study eligibility, we will approach the parents/LAR for informed consent. The PI will verify the status of who has been appointed the subject's guardian or LAR. Due to the nature of ASBI, we assume all children will be incapable of assenting to this study. Once the parent(s) / LAR have consented for their child to participate in the study, the CFS scores will be calculated to confirm study eligibility. The families will be told that their child does not qualify for the study if they do not meet the CFS scoring criteria. We expect 20 parent/child dyads to

## Protocol Summary/Submission Application

complete the study. If the patient does meet CFS scoring criteria for study enrollment, we will collect the CFS score for a 12-hour period before placement of the device followed by every 12 hours while the device is in place and for an additional 72 hours after removal of the device.

**Data collection & Management:** We will collect demographics, cause of ASBI, imaging findings, sedative, pain and other neurotropic medications, and maintenance and rescue medications for PSH including their number and doses for every 24-hour period from placement of the device. We will also collect all the HRV and pupillometry parameters for the 12-hour period before and after placement of the device. For the historical cohort, we will collect demographics, cause of ASBI, imaging findings, maintenance and rescue medications used in each 24 hour period for the first 120 hours and then additional 72 hours from the time of meeting CFS score > 6 criteria. . The REDCap database for this study will be developed and managed by Quantitative Health Sciences on MCW-secure servers

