### **Aim 1: Identify and enroll 20 pediatric patients with ASBI and PSH.**

**Methods:** Parent(s)/legal guardians, 18 years or older, will be approached for informed consent if their child has ASBI and is exhibiting clinical signs and symptoms of PSH. Once consented, the CFS scoring tool (Table 1a,) will be used to evaluate patients felt to be exhibiting symptoms of PSH to identify eligible ASBI patients. Patients with CFS score > 6 will be eligible for enrollment in the study.

Families of patients who do not meet the CFS score criteria > 6 will be told their child did not meet scoring criteria of study and will be considered consented but not enrolled in study.

Study Enrollment is defined as meeting CFS criteria of > 6 after consent. If CFS scores are already being collected for subject prior to subject consent as a standard of care, we can use already available CFS scores from medical record. The PENFS device will be placed over the external ear by study investigator or one of trained nurses (RNs) from the Pediatric Translational Research Unit (P-TRU) within 24 hours of meeting CFS > 6 score criteria..

There are 380-400 PICU admissions/year that are seen by ICU Neurology. Using a conservative estimate of 8-10% incidence of PSH, we expect to have 35-40 patients with PSH. At a conservative 60% enrollment rate, we expect to be able to successfully enroll 20 patients in this pilot study. Previous studies using the device has shown it to be well-tolerated with minimal side effects (25,26). In a large, randomized sham-controlled trial Kovacic et al showed a very low rate of discontinuation of the device due to side effects. We hypothesize that the dropout rate will be ≤ 10%. Tolerability of the device will be assessed by subjective assessments of device tolerance by the bedside nurse, the CFS score (increasing score after device placement would suggest worsening PSH symptoms) and skin integrity (bedside nurses will perform routine skin evaluation and care while the device is in place.). To evaluate safety, we will monitor for serious adverse effects such as cardiac dysrhythmia (EKG monitoring), and new-onset seizures.

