### Section 2 Regulatory Criterion for Approval: Benefits

**Risks to subjects are reasonable in relation to anticipated benefits, if any, to subjects, and the importance of the knowledge that may reasonably be expected to result. In evaluating risks and benefits, the IRB should consider only those risks and benefits that may result from the research (as distinguished from risks and benefits of therapies subjects would receive even if not participating in the research).**

➤ If there is no benefit and no knowledge to be gained, there is no justification to expose subjects to risk.

**Protocol Summary/Submission Application****A. Describe the potential benefits to science and/or society which may accrue as a result of this research:**

If found to be effective in treatment of PSH, the PENFS device will offer a non-medication modality for treatment of PSH thus helping to decrease the need for neurosedative medications and decreasing the adverse effects of the medications.

The natural history of PSH is that the symptoms are worse initially requiring multiple medications to ameliorate the symptoms. Over time, the PSH symptoms decrease allowing weaning of some of the medications. Thus, the PENFS device might offer significant benefit in the initial period helping to limit the number of medications needed to control the symptoms of PSH.

**B. Are there any benefits which may accrue to the individual subjects in this research (compensation is not considered a benefit)?**

No  Yes

If YES, describe: Improvement in PSH symptoms and reduction in need for medications to treat PSH could potentially decrease the adverse effects associated with use of these medications.

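### Aim 3b lists no time since injury or PSH onset for either cohort and no index CFS for historical children, and the two cohorts' clocks start at different events

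*Combined protocol and SAP*

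**What the plan says.** Section E, Data collection & Management, gives one list per cohort. For device children: "We will collect demographics, cause of ASBI, imaging findings, sedative, pain and other neurotropic medications, and maintenance and rescue medications for PSH". For historical children: "For the historical cohort, we will collect demographics, cause of ASBI, imaging findings, maintenance and rescue medications used in each 24 hour period". Device children also have a starting severity score ("we will collect the CFS score for a 12-hour period before placement of the device"). The historical list has none; there, CFS appears only as the event that starts the clock.

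The clocks are defined in the same paragraph. Device-cohort drug use is counted by "number and doses for every 24-hour period from placement of the device", and historical drug use "from the time of meeting CFS score > 6 criteria". Under Aim 1, "Study Enrollment is defined as meeting CFS criteria of > 6 after consent", although routine scores already in the chart may be used, and the device goes on "within 24 hours of meeting CFS > 6 score criteria".

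Section 2, item A, describes PSH as worst at the start and then easing: "Over time, the PSH symptoms decrease allowing weaning of some of the medications".

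For Hypothesis 3b the analysis overview plans a t-test or Mann-Whitney against the historical data, then a classification tree using demographics, clinical history (not defined) and PENFS use. The Aim 3b statement says the comparison is to support the power calculation for a later efficacy trial.

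**The concern.** The Aim 3b outcome is medication use, and the protocol itself says the need for medication changes with time in the illness. When two non-randomised groups are compared on such an outcome, the analyst needs to know where each child was in that course, and how ill, when counting began. The planned dataset does not show this for historical children and shows only the severity part for device children. The planned test makes no adjustment.

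What is at stake is the estimate. Aim 3b is declared as lacking power for efficacy, so no efficacy claim hangs on it. The estimated difference is nevertheless meant to feed the next trial's sample size. A bias in it would carry over, and small numbers do not excuse a bias.

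**Working it through.** The plan gives no figure to reproduce here: the 20 patients are a convenience sample and the historical cohort's size is not stated. The check is a comparison of the two lists and clocks, then an illustration of scale.

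**1. Lists and clocks (Section E and Table 3)**

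| Item | Device children | Historical children |
|---|---|---|
| Time of injury or arrest | not listed | not listed |
| Time of PICU admission | not listed | not listed |
| Time of PSH onset | not listed | not listed |
| CFS value at the start | 12 hours before placement | not listed |
| Clock starts at | device placement | meeting CFS > 6 |

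**2. Offset between the clocks.** Measured from the first CFS > 6, a device child's start is delayed by

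offset = (placement − qualifying score) + (qualifying score − first CFS > 6).

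The first term is 0 to 24 hours (Aim 1). The second is zero or more, because the qualifying score normally follows consent and need not be the first above 6; the documents set no limit on it. Reading the historical clock as starting at the first CFS > 6 (the text does not say first), device children can only start at the same point or later. Aim 3b counts drugs in 24-hour bins, so a full 24-hour lag lines up the device cohort's first bin with the historical cohort's second.

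**3. Severity above the threshold.** With diastolic pressure left out, the paediatric scale has six items scored 0 to 3, a maximum of 6 × 3 = 18. Eligible children run from 7 to 18, across both the moderate (7-12) and severe (13 or more) bands of Table 1a. Sharing a threshold does not balance what lies above it.

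**4. Scale, assuming an inert device.** If drug need falls by a proportion r per day and device children start L days later, the apparent reduction is s = 1 − (1 − r)^L. The protocol gives no rate, so r = 5% to 10% is an assumption. L of up to 1 day is the documented lag.

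- L = 0.5: 1 − 0.95^0.5 = 2.5%; 1 − 0.90^0.5 = 5.1%.
- L = 1: 1 − 0.95 = 5%; 1 − 0.90 = 10%.

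**5. Effect on the test.** Take two-sided alpha 0.05, a coefficient of variation (CV) of 0.5 to 1.0, 20 device children and m = 20 or 40 controls (alpha, CV and m are assumptions). Then SE = CV × √(1/m + 1/20), and the rejection probability is Φ(s/SE − 1.96) + Φ(−s/SE − 1.96). For s = 10%, CV = 0.5 and m = 40: SE = 0.5 × √0.075 = 0.137, s/SE = 0.73, and the probability is 11.3%. Over all combinations at L = 1 and r = 5-10%, it runs from 5.3% to 11.3% against a nominal 5%. At the documented lag, the effect on the test is modest.

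**The case against.** **Not listed is not the same as not collected.** Section E is a narrative, the REDCap forms are not shown, Aim 3b provides for open-ended abstraction at chart review, and the classification tree takes clinical history as an input. This stands as a limit on the wording, but none of these names either variable. A reader might infer that adjustment will be impossible later. The documents do not support that: Section 7 keeps a key linking study ID to record number, and Section 3 collects historical record numbers, so the charts could be reopened.

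**Both cohorts are tied to CFS > 6.** This partly aligns disease phase, and a score must be worked out for each control to set time zero. It leaves severity above 6 and the clock offset unaddressed.

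**The direction is open.** A reader might infer that the bias must favour the device, because its clock starts later. Other features could pull the opposite way. Section E expects many consented children to fail the CFS criterion, which may select persistent or severe cases. Maintenance drugs begun before placement are allowed, which may raise device-cohort counts.

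**The size is open too.** A reader might suppose lags of several days and correspondingly large distortions. The only documented lag is up to 24 hours; longer ones are possible, but nothing in the text gives them. Section 2 also states no rate of decline, and does not say whether time runs from injury or from PSH onset.

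**It is a pilot with historical controls.** Such comparisons are always confounded, and the protocol acknowledges that randomising would be better. That is fair, but it does not justify leaving out a measurable factor that the protocol itself identifies.

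**Conclusion.** The point holds as a gap in what is listed and pre-specified for Aim 3b. Neither cohort has a recorded position in the course of the illness, controls have no listed starting severity, the clocks differ by a documented 0 to 24 hours or more, and the main comparison is unadjusted. A difference in doses could reflect disease phase or severity as well as the device, in a direction that is not established.

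The size is known only by assumption: up to 5-10% fewer doses at a one-day lag if need falls 5-10% a day. Any imbalance in days since injury or in index CFS would come on top and cannot be sized from the documents. The feasibility and tolerability aims are untouched. The harm is a biased planning estimate, and the correction is worth making before abstraction begins.

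**What to change.** - For both cohorts, record the date and time of injury or arrest, PICU admission, first documented PSH and first CFS > 6, together with the index CFS. That score is already taken for device children and is needed to set time zero for controls.
- Use one time-zero definition in both cohorts for Aim 3b, or keep the present clocks and report the offset. If first CFS > 6 is chosen, device-cohort drug data must reach back to it; Table 3 currently starts drug collection 12 hours before placement, while the permitted lag is 24.
- Report the distributions of these times and of index CFS by cohort. Adjust for, or match on, days from injury (or PSH onset) and index CFS, and name these as covariates in the Hypothesis 3b text.
- State that residual confounding from a non-randomised historical control remains, and repeat that caveat wherever the estimate is used for planning.

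The cost is some abstraction time from charts already being opened one by one, and two covariates in a sample with only 20 device children. Whether matching is practical cannot be judged yet: the historical cohort's size is not given, and Section 3 describes its search by broad TBI criteria, which may narrow the pool.
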